In 2016, the United States Centers for Disease Control and Prevention (CDC) issued the "CDC Guideline for Prescribing Opioids for Chronic Pain" which encourages the use of alternatives to opioids and other practices that minimize harm to patients [6]. Despite the introduction of this guideline, primary care clinicians, who prescribe 45% of all opioid prescriptions in the US, report practical challenges in implementing these recommendations [7]. The dynamics of opioid use make following guidelines difficult. Since opioid analgesia from a given dose declines with chronic use due to tolerance, doses end up increasing the chance of harm. Over time, the primary benefit of opioids for many patients is the avoidance of withdrawal. As patients become dependent on opioids, they may misconstrue the easing of withdrawal hyperalgesia that occurs with the consumption of opioids as ongoing effectiveness, and they may become reluctant to stop opioids [8]. More cautious opioid prescribing (including fewer new starts, avoidance of high doses, and slow, collaborative tapers for those already on high dose long-term therapy) may improve the balance of benefits and harms for patients with chronic pain. To become a more cautious prescriber, a clinician may need to be informed that opioid risks are present and relevant to his or her own patients.

A prior quality assurance study found that clinicians judge risk to patients as greater after information about a patient's fatal overdose is available to them [9]. Of course, not all clinicians prescribe to patients who suffer a fatal overdose, so the question remains whether providing feedback concerning non-fatal overdoses will have a similar impact on prescribing clinicians. Thus, the Application of Economics & Social psychology to improve Opioid Prescribing Safety (AESOPS) Availability of Harm trial will test whether or not providing feedback to clinicians on both fatal and non-fatal overdoses results in more judicious prescribing of opioids. The objective of the AESOPS Availability of Harm trial is to dampen the intensity and frequency of opioid prescribing in accordance with the Centers for Disease Control and Prevention recommendation to "go low and slow". We

aim to accomplish this by increasing the mental availability of risks associated with opioid use by notifying clinicians of harmful patient outcomes.

B. Method of Study in Detail

a) Purpose and hypotheses to be tested:

Study Synopsis

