1. Clinicians randomized to the overdose notification group will exhibit a greater reduction in weekly MME from the pre- to post-period compared to clinicians randomized to the control group for fatal and non-fatal overdoses.
2. Among the clinicians who prescribed at least one opioid in the study period, those randomized to the overdose notification group will exhibit a greater reduction in the proportion of a clinician's patients prescribed at least 50 daily MME from the pre- to post-period compared to clinicians randomized to the control group for fatal and non-fatal overdoses.

b) Number of subjects:

AltaMed Health Services is a private health system in Los Angeles, California. AltaMed has 35 clinics with 134 clinicians with 17,674 such patients. Clinicians meeting inclusion criteria will be enrolled in the study. Northwestern Medicine is a regional health system affiliated with an academic medical center located in the Chicago region of Illinois and includes 60 primary care clinics that contain 387 clinicians with 12,552 patients using chronic opioid therapy for noncancer pain—on opioids for greater than three months.

c) Mechanism for subject selection or exclusion:

Eligible physicians and patients will be identified using outpatient opioid prescribing data

from electronic medical records. A clinician is eligible for inclusion if: 1) s/he prescribed a qualifying scheduled drug to a patient in the 12 months prior to their fatal or non-fatal overdose 2) the patient is 18 years old or older at the time of the overdose, 3) s/he practices within a health system enrolled in the study, and 4) the overdose occurs during the 12-month observation period.

A patient is eligible for identification in a physician notification if s/he (a) has been prescribed an opioid by an eligible clinician (b) has a documented overdose event in EHR or mortality data. Patients without overdose events will be excluded. Patients with fatal overdoses in Los Angeles County will be excluded to avoid redundancy with existing notification practices.

[figure not shown]
d) Duration of intervention:

The duration of the overdose notification intervention is one day.

e) Total duration which study will be performed (data collection, intervention, and analysis period):

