HIPAA Limited Data Set. At the conclusion of the study period, each health system will prepare a HIPAA limited data set for analysis. The data set will include dates of overdose events, post-intervention opioid prescribing, and unique study identifiers. Study assignment, physician notification information, and overdose data from Los Angeles County Department of Public Health will be de-identified retaining unique study identifiers. Data will be transferred to USC Schaeffer Center HIPAA data enclave for analysis. No USC study personnel will have access to any patient identifying information. Links between identified data and study identifiers will be destroyed at the conclusion of the analysis.

C. List of Experimental Procedures to be Employed

a) List and detail risks:

- Mitigation of risk to participating physicians
 - Letters are a normal aspect of quality review. Letters notifying clinicians of a fatal overdose are mandated in Los Angeles County. [see LA County Board of Supervisors Meeting <https://youtu.be/hBefHyAL5I8>]. Therefore, risks faced by participants do not exceed that of normal clinical practice. We will take every precaution to mitigate risk to participating clinicians by keeping this disclosure private. All correspondence will be private and conducted through delivery using one of the following approaches: 1) US Postal Service, 2) institutional email, or 3) Epic inbox message, and will not be shared outside of the study.
- Mitigation of risk to patients
 - Risk of correspondence adds no additional risk compared to what is already being sent in the mail or by email (such as prior authorization letters by insurers or billing). Further, the HIPAA conduit exception allows HIPAA-covered entities to use the US Postal Service, institutional email, and Epic inbox messaging for the transmission of personal health information. US Letters and email are private and tampering with private mail is a federal offense.
 - The NIH has established a Data and Safety Monitoring Board for this study. The board consists of individuals with expertise in opioids, overprescribing, biostatistics or research methods. When notified of an unanticipated event following the intervention, the board will convene and make a decision as to whether the study should continue.
 - A potential risk is an adverse event, defined by the CDC as an abrupt

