discontinuation of opioids for persons whose most recent prescription exceeds 49 MME daily dose; or as reported to study staff (10).

If there is a significant difference in the prevalence of these adverse events or overdoses between the treatment and control groups, the differences will be reported to the Data and Safety Monitoring Board and in the publication of the study results. *It is important to note that prior quality evaluations of these letters observed no additional risk of abrupt changes to opioid prescribing upon receipt of a letter (<https://pubmed.ncbi.nlm.nih.gov/30093595/>).*

- Management of overdose and prescribing data poses no more than minimal privacy risks. USC, health systems and IDPH comply with all local and federal security regulations protecting privacy. Identified patient data will be destroyed after the notifications have been prepared. A HIPAA Limited Data Set that includes outpatient prescribing records, overdose events, and notification status will be transferred to USC for data analysis in USC's HIPAA compliant enclave.

b) Experimental Procedures:

Randomization and Allocation. Overdose clusters are the units of randomization in this study. A cluster consists of all clinicians who prescribed one or more of the included scheduled drugs to the patient in the year prior to the overdose. Overdose clusters will be randomized to the overdose notification group or the control group, stratified by the health system which defines the cluster in the year prior to the overdose event.

Allocation will be concealed until after the study groups are assigned. Clinicians who practice at multiple clinics will be assigned to the clinic at which the majority of their visits occurred in the year prior to the overdose event. If clinicians belong to more than one cluster (have multiple patients with opioid-related overdoses), they will be randomly assigned to one of those patients and placed in the corresponding study group. If clinicians belonging to more than one cluster are randomized to the intervention group, they will only receive an overdose notification regarding the one patient to whom they were randomly assigned.

Intervention. Clinicians in the intervention group receive a letter notifying them of their patient's fatal or non-fatal overdose. As described above, we will identify overdoses from electronic health record data from emergency departments and state vital records.

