2. **Avoid opioid prescribing for chronic pain and avoid/minimize opioid prescribing for acute pain.** According to the Centers for Disease Control and Prevention (CDC), clinicians should avoid opioids for chronic pain, and when necessary for acute pain, start with the lowest effective dose of immediate-release opioids. Three days or less is often sufficient to address acute pain. Opioids should not be considered first-line

or routine therapy for chronic pain.

3. **Taper opioids to safer doses.** The CDC recommends that for patients already on long-term high-dose opioid therapy, taper to a dose that is lower than 50 morphine milligram equivalents (MME) and consider slow opioid tapers as well as pauses in the taper if needed for long-term users.
4. **Avoid “the 90-day cliff.”** One California study found that nearly 70% of patients who died of prescription-related overdoses were prescribed scheduled drugs for 3 consecutive months.¹ The CDC recommends opioids should be discontinued if benefits do not outweigh risks (if realistic goals for pain and function have not been met).
5. **The CDC recommends prescribing naloxone** to patients on higher than 50 MME of opioids per day.
6. **Prescribed medications for opioid use disorder.** Clinicians should offer medications for opioid use disorder, such as buprenorphine/naloxone, to their patients with opioid use disorder. Physicians, physician assistants, and advanced practice nurses can file a waiver to prescribe buprenorphine for the indication of opioid use disorder by visiting the SAMHSA website (<http://www.samhsa.gov/medication-assisted-treatment/become-buprenorphine-waivered-practitioner>) or by calling SAMHSA at [contact]. On April 28, 2021, SAMHSA announced that it will waive the training requirement for physicians, physician assistants, and advanced practice nurses to become waivered to prescribe buprenorphine for the indication of opioid use disorder. Further, you can use the Epic Social Determinants of Health (at the bottom left of your Storyboard), click on “Select Community Resources”, and find “Substance Use” resources.

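### Abrupt stops in long-term patients at or below 49 MME are not systematically counted as harm, although the letters' stop advice and the primary outcome carry no dose limit

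*Combined protocol and SAP*

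**What the plan says.** **Letters (Appendices 2 and 3, items 2 to 4, same text in both).** Item 2 is headed "Avoid opioid prescribing for chronic pain and avoid/minimize opioid prescribing for acute pain". Item 4 says "The CDC recommends opioids should be discontinued if benefits do not outweigh risks (if realistic goals for pain and function have not been met". Neither names a dose. Item 3, the only item on tapering, is addressed as follows: "for patients already on long-term high-dose opioid therapy, taper to a dose that is lower than 50" MME; it goes on to mention slow tapers and pauses for long-term users. The closing paragraph asks the clinician to use all six items with the next patient who has pain, so the advice is not confined to the patient who overdosed.

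**Outcome (section B, Study Synopsis; Hypothesis 1).** The outcome is the pre-to-post change in a clinician's weekly MME over all patients. There is no dose floor.

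**Harm (section C.a).** The plan names one adverse event, which it attributes to the CDC. It concerns stopping that is abrupt, and its dose limb reads "discontinuation of opioids for persons whose most recent prescription exceeds 49 MME daily dose". The sentence then adds a second limb, events reported to study staff, with no dose threshold. Differences between arms in these events, or in overdoses, go to the Data and Safety Monitoring Board and into the publication.

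**Population (section B.b).** Northwestern's 12,552 are described as "patients using chronic opioid therapy for noncancer pain", defined by more than three months of use and not by dose.

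**The concern.** Benefit and harm are counted over different patients. If a clinician who has read items 2 and 4 abruptly stops a long-term patient at or below 49 MME, the clinician's weekly MME falls and the stop contributes to the primary result. The record-based harm criterion does not look at that patient. If the trial then reports that abrupt discontinuation did not differ between arms, readers will take this as covering the patients whose prescribing changed. For lower-dose long-term patients it would rest on no systematic count.

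**Working it through.** The plan gives no figure on this point to reproduce. The check sets the texts side by side and then illustrates the size.

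**1. Dose limits, element by element**

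| Element | Dose limit |
|---|---|
| Letter item 2 (avoid) | none |
| Letter item 3 (taper) | opens with long-term high-dose patients |
| Letter item 4 (discontinue) | none, but conditional on benefit and risk |
| Primary outcome | none |
| Harm, record-based limb | most recent prescription above 49 MME daily |
| Harm, reported limb | none |
| Overdose comparison | none |

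**2. How far the two routes without a dose limit reach.** Reports to study staff depend on someone knowing where to report. Section E says the design requires that physicians not know they are research participants, both letters say no reply is expected, and no active reporting procedure is described for either arm. The overdose comparison sees an abrupt stop only if an overdose follows.

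**3. Timing of the dose.** The criterion uses the most recent prescription without saying relative to what date. If it is read after the letter, a patient tapered below 50 MME and then stopped abruptly also drops out of the count. Membership of the at-risk group would then depend on the intervention, and the comparison between arms could be biased.

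**4. Illustration of size.** Inputs from section B.b: 17,674 patients at AltaMed and 12,552 at Northwestern, total 17,674 + 12,552 = 30,226. These describe the two systems, not the patients of randomized clinicians, so the total is only a frame. The share *s* at or below 49 MME is not in the documents and is assumed to be 50% to 90%. Abrupt-stop risk is assumed to be 5% in control and 8% in the letter arm at every dose.

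- Patients outside the record-based limb = 30,226 × *s*
- Excess stops at all doses = 1,000 × (0.08 − 0.05) = 30 per 1,000 long-term patients
- Excess captured = 30 × (1 − *s*)

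| *s* | Outside the limb | Captured of 30 | Not captured |
|---|---|---|---|
| 50% | 15,113 | 15 | 15 |
| 70% | 21,158 | 9 | 21 |
| 90% | 27,203 | 3 | 27 |

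Under this uniform effect, and with the dose taken before the letter, the existing measure still estimates the 3-point difference correctly for patients above 49 MME. It says nothing about the others.

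The limiting case puts the whole effect below the threshold: 4% against 8% there, and 4% in both arms above it. The uncounted excess is then 1,000 × *s* × (0.08 − 0.04) = 20, 28 or 36 per 1,000 at *s* = 50%, 70% or 90%, with a measured excess of zero. That zero is built into the assumptions and is a bound, not an expectation.

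**The case against.** - **The definition has other routes.** A reader might infer that a stop at or below 49 MME cannot register as harm at all. The documents do not support that: the reported limb and the overdose comparison have no dose threshold, and the Board convenes when notified of an unanticipated event. This stands, and it limits the point to what is systematically counted.
- **The letters are narrower than they first look.** A reader might also infer that stop advice reaches every chronic-pain patient. It does not. Only intervention-arm clinicians get a letter, item 4 is conditional, part of item 2 concerns starting therapy, and no item advises stopping abruptly. Item 3's closing words on slow tapers can be read as covering long-term users generally.
- **Controls also receive advice without a dose limit.** The CDC pocket guide discourages opioids as first-line treatment for chronic pain and makes continuation depend on improvement. This stands, so a difference between arms cannot be presumed. It can go the other way too: the guide's taper advice is not confined to high doses, whereas the letters' taper item opens with high-dose patients.
- **The threshold is adopted, not accidental.** Section C.a attributes it to the CDC, and it sits beside the 50 MME line in the secondary outcome. That is a reason to keep the measure. It does not extend what the measure can show.
- **No contradiction with the stated aim.** It is tempting to set items 2 and 4 against the Background's description of cautious prescribing, "fewer new starts, avoidance of high doses, and slow, collaborative tapers for those already on high dose long-term therapy". That list is introduced as examples, and conditional discontinuation is not abrupt discontinuation. No contradiction is shown.

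**Conclusion.** The point holds as a gap in coverage. The one harm criterion that can be run on prescribing records stops at 49 MME, while the avoid and discontinue advice and the primary outcome do not. Abrupt stops in long-term patients at or below 49 MME are therefore not systematically counted, and a null result on abrupt discontinuation would not apply to them.

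The reading of the texts needs no assumption. The size does: the documents give neither a dose distribution nor stop rates, so the figures of 15 to 27 uncounted per 1,000 (20 to 36 in the limiting case) are illustrations. The existing measure remains valid for its own group if the dose is taken before the letter. This is a worthwhile, inexpensive improvement to the safety analysis, not a flaw in the primary comparison.

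**What to change.** In section C.a:

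1. Keep the above-49 MME measure as it is.
2. Add a descriptive tabulation, by arm, of abrupt discontinuation among patients on opioids for more than three months at the letter date (for controls, the corresponding mailing date). Show two bands separately: 49 MME or below, and above 49 MME. Both cut-points are the protocol's own.
3. Fix each patient's band from the last prescription before the letter, so that the intervention cannot move patients between bands.
4. Write one record-based rule for what counts as abrupt, which the protocol does not now give, and apply it identically in both arms and both bands.
5. Limit the published safety conclusion to the bands reported.

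**Cost.** A short addition to C.a and one further row in the safety table. No new data should be needed: outpatient prescribing records already go into the analysis data set, the primary outcome needs the six months before the letter, and the existing harm measure needs patient-level prescriptions. The rule for abrupt takes some work.

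**Downside.** Lower-band events may be milder and noisier, because intermittent use, end of need or a change of prescriber can look like a stop. Hence separate bands and a descriptive role. No clinical threshold and no change to the letters is proposed.

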Appendix 3. Nonfatal Overdose Notification Letter to Clinician

Dear (Name of Prescriber),

This is a courtesy notification to inform you that your patient, {Name, Date of Birth}, visited the Emergency department on {Date} with a nonfatal opioid overdose.

Northwestern Medicine is tracking outcomes for patients on opioids and other scheduled drugs.

A significant proportion of overdoses are due to the combination of opioids with a sedative medication. Patients may obtain legitimate prescriptions for opioids, benzodiazepines, muscle relaxants, and sleep aids from more than one prescriber. When taken in any combination, these medications put patients at greater risk of overdose and death. Many fatal and non-fatal overdoses are a result of long-term therapeutic prescribing or of combined prescription medications with drugs obtained from other sources.

Our aim is to alert clinicians to the potential dangers of opioid medications and how common death from misuse of these medications is in Chicago and throughout Illinois.

Northwestern Medical Group would like to remind you that Illinois has a prescription drug monitoring program called the Illinois Prescription Monitoring Program (ILPMP) which *helps prescribers avoid prescribing controlled substances when they are likely to do more harm than good.*

ILPMP contains information about whether and when other clinicians have prescribed controlled substances to your patient within the last 12 months. With few exceptions, prescribers are required by state law to check the ILPMP when prescribing opioids. **Review of the ILPMP could alert you to problematic medication usage, potential addiction or diversion, and help inform safe medication prescribing and monitoring.** This information is available through Epic and at <https://www.ilpmp.org/CDC/login.php>.

Emergency department visits for an overdose strongly suggest a diagnosis of opioid use disorder. The one-year mortality following an opioid overdose is high at 10%. If your patient's overdose was due to opioid use disorder, medications for opioid use disorder, such as buprenorphine/naloxone, can be safely prescribed in any setting of care and greatly reduce mortality risks through prevention of future overdose. Medications for opioid use disorder improve your patients' chances of recovery.

You may show your commitment to being a safe prescriber by using the following evidence-based interventions to lower overdose rates:

1. **Avoid co-prescribing** an opioid and a benzodiazepine. Opioids and benzodiazepines can have additive central nervous system depressant effects.

2. **Avoid opioid prescribing for chronic pain and avoid/minimize opioid prescribing for acute pain.**
According to the Centers for Disease Control and Prevention (CDC), clinicians should avoid opioids for chronic pain, and when necessary for acute pain, start with the lowest effective dose of immediate-release opioids. Three days or less is often sufficient to address acute pain. Opioids should not be considered first-line or routine therapy for chronic pain.
3. **Taper opioids to safer doses.** The CDC recommends that for patients already on long-term high-dose opioid therapy, taper to a dose that is lower than 50 morphine milligram equivalents (MME) and consider slow opioid tapers as well as pauses in the taper if needed for long-term users.
4. **Avoid “the 90-day cliff.”** One California study found that nearly 70% of patients who died of prescription-related overdoses were prescribed scheduled drugs for 3 consecutive months.ⁱⁱ The CDC recommends opioids should be discontinued if benefits do not outweigh risks (if realistic goals for pain and function have not been met).
5. **The CDC recommends prescribing naloxone** to patients on higher than 50 MME of opioids per day.
6. **Prescribed medications for opioid use disorder.** Clinicians should offer medications for opioid use disorder, such as buprenorphine/naloxone, to their patients with opioid use disorder. Physicians, physician assistants, and advanced practice nurses can file a waiver to prescribe buprenorphine for the indication of opioid use disorder by visiting the SAMHSA website (<http://www.samhsa.gov/medication-assisted-treatment/become-buprenorphine-waivered-practitioner>) or by calling SAMHSA at [contact]. On April 28, 2021, SAMHSA announced that it will waive the training requirement for physicians, physician assistants, and advanced practice nurses to become waivered to prescribe buprenorphine for the indication of opioid use disorder. Further, you can use the Epic Social Determinants of Health (at the bottom left of the Storyboard), click on “Select Community Resources,” and find “Substance Use” resources.

When your next patient presents with pain, keep the above 6 recommendations close at hand to assist with their safe care. Also, be comfortable voicing your concern about prescribing safety with them so that they are also aware of the dangers associated with scheduled drugs. We also encourage you to routinely log into ILPMP and learn more about the prescriptions your patient received leading up to the overdose.

This letter is meant to be informative only and there is no expectation of reply. We understand that learning of your patient’s overdose can be difficult. We hope that you will join us in our effort to prevent future drug overdoses. Please take this as an opportunity to talk with your patient and perhaps other patients in your practice who may be at-risk.

Sincerely,

[Medical Director or similar role]

ⁱ Lev, R., Petro, S., Lee, O., Lucas, J., Stuck, A., Vilke, G. M., & Castillo, E. M. (2016). A description of Medical Examiner prescription-related deaths and prescription drug monitoring program data. *The American journal of emergency medicine*, 34(3), 510–514.
<https://doi.org/10.1016/j.ajem.2015.12.023>

PRESCRIBING OPIOIDS FOR CHRONIC PAIN

ADAPTED FROM CDC GUIDELINE

Opioids can provide short-term benefits for moderate to severe pain. Scientific evidence is lacking for the benefits to treat chronic pain.

IN GENERAL, DO NOT PRESCRIBE OPIOIDS AS THE FIRST-LINE TREATMENT FOR CHRONIC PAIN (for adults 18+ with chronic pain > 3 months excluding active cancer, palliative, or end-of-life care).

BEFORE PRESCRIBING

